### **16.3.3. Primary Endpoint Analysis**

The primary endpoint (change of TSQM-9 convenience domain at week 12) will be analysed by a repeated measures analysis of variance adjusted for baseline factors (age, sex, disease duration, previous treatment duration, EDSS).

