Data for estimating the sample size were derived from studies reporting the distribution (mean value and standard deviation) of the TSQM-9 in MS patients treated with IFN (9). Assuming an average value of the overall convenience domain at baseline of 55 (SD=16) (9), with 250 subjects we have a power of 90% to detect a change of 3 points on the overall convenience domain (from 55 to 58) under the conservative hypothesis of a SD=16 (9) for the difference between baseline and week 12. However, by assuming a drop-out rate up to 10% during the study, we consider it appropriate to enrol a total of 275 patients.

7. Software

The analysis will be performed using the software Stata version 14.0.

8. Variables for analysis

This section contains definitions and conventions that will be used for the analysis.

Demographic and baseline characteristics

Demographic (age, gender, education and employment) and medical information (disease duration, previous treatments, comorbidities and concomitant therapies, EDSS score and number of relapses in the previous 12 months) will be obtained at baseline.

Efficacy

Being this a health outcomes research study, the term efficacy refers to the assessment of the following patients' reported parameters, corresponding to the primary and secondary objectives of the study, and to the measurement of the related endpoints:

- overall treatment satisfaction;
- injection system satisfaction;
- adherence to treatment;
- health-related quality of life;
- fatigue.

All the endpoint-related questionnaires, described below, will be administered at baseline and after 12 and 24 weeks of treatment.

Primary variables

a) Patients' Satisfaction assessment

- *Abbreviated Treatment Satisfaction Questionnaire to Medication (TSQM-9)*

The TSQM Version 1.4 is a 14-item psychometrically robust and validated instrument consisting of four scales. The four scales of the TSQM include the effectiveness scale (questions 1 to 3), the side effects scale (questions 4 to 8), the convenience scale (questions 9 to 11) and the global satisfaction scale (questions 12 to 14). In the TSQM-9, the five items related to side effects of medication were not included, which creates a need to psychometrically assess the performance of the abbreviated instrument.

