In addition, routine clinical assessments will be performed in order to check the safety of the Peg-IFN ongoing treatment.

Laboratory Safety Assessments

At the Investigator's discretion, the following routine laboratory tests can be carried out, in order to monitor the safety profile of the ongoing treatment based on Peg-IFN:

- Hematology: RBC- WBC –Haemoglobin- Haematocrit- MCV- MCH – MCHC - Platelets Count – Lymphocytes- Monocytes – Neutrophils – Eosinophils – Basophils
- Blood chemistry: creatinine, blood urea nitrogen (BUN), alkaline phosphatase, ALT, AST, gamma-glutamyl-transferase (GGT).

A pregnancy hCG test (blood sample) will be performed at the baseline visit (T0) to exclude pregnancy, if applicable (it is not required if the subject is post-menopausal or surgically sterilized).

9. Missing data

For missing data in TSQM-9, MSTCQ and MusiQoI see paragraph Variable of analysis.

For the other variables no imputation technique will be apply.

10. Statistical analysis

The primary and secondary endpoints will be evaluated using a repeated measures ANOVA. The repeated measures ANOVA is used to compare group means on a dependent variable across repeated measurements of time. This statistical method is used for making simultaneous comparisons between two or more means of two or more related, not independent, groups.

However, in addition, it could be useful to apply a general linear mixed model that models for group means as fixed effects while simultaneously modeling for individual subject variables as random effects (12). This kind of model is a subject-specific model and is a choice for analysing longitudinal data. Unlike the repeated measures ANOVA, which requires a complete balanced array of data, the mixed model can accommodate a dataset with a large portion missing. Although the repeated measures ANOVA requires a fixed time schedule among all individual units, the mixed model can accommodate flexible time schedules. Furthermore, rather than treating time as a categorical variable, as in the repeated measures ANOVA, the mixed model is capable of treating time as either a continuous variable or a categorical variable or both.

Spearman's correlation coefficient measures the strength of association between two ranked variables.

Differences will be considered statistically significant if the p-value will be less or equal to a type I error =0.05 (two-sided test).

11. Efficacy data

a. Primary Endpoint Analysis

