The primary endpoint is to evaluate the changes from baseline in the score of convenience satisfaction domain of TSQM-9 at 12 weeks. (*Stata instruction: anova var1 time, repeated(time)*)

b. Secondary Endpoints Analysis

- Changes from baseline in the score of all domains of TSQM-9 at 24 weeks;
- Changes from baseline in patient adherence to study treatment survey at 12 and 24 weeks;
- Changes from baseline in the score of FSS (Fatigue Status Scale) at 12 and 24 weeks;
- Changes from baseline in the score of Adapted Sclerosis Treatment Concerns Questionnaire (MSTCQ) at 12 and 24 weeks;
- Changes from baseline in the score of Multiple Sclerosis International Quality of Life questionnaire (MusiQoL) at 12 and 24 weeks;
- Changes from baseline in clinical measures (ARR, percentage of relapse-free patients), measures at 24 weeks.

All the above primary and secondary endpoints will be analysed by a repeated measures analysis of variance adjusted for baseline factors (age, sex, disease duration, previous treatment duration, EDSS) (*Stata instruction: anova var1 var2 time, repeated(time)*).

Correlations between variables will be assessed by a Spearman rank correlation coefficient (*Stata instruction: spearman var1 var2*).

[figure not shown]
To evaluate the relationship between patients' satisfaction and social-demographic factors (age, sex, employment working, level of education, etc.) and clinical characteristics (ARR, disability, etc.) generalized linear mixed models for repeated measurements will be performed (*Stata instruction: mixed var1 var2 || patient:*).

12. Safety Data

a. Adverse events

All events will be coded using the Medical Dictionary for Regulatory Activities (MedDRA). Type and incidence of all AEs will be tabulated. Severity and drug relatedness of all reported AEs will be tabulated.

b. Clinical Laboratory Tests

	Statistical Analysis Plan Protocol N. BIIT0215– Platinum	Pag. 14 di 18
---	---	---------------

For the clinical laboratory data, descriptive statistics will be generated for all tests performed. Laboratory abnormalities will be determined in accordance with the normal ranges of the clinical laboratory. Laboratory abnormalities will be tabulated.

13. Tables

The following tables will be repeated for each visit, if applicable.

- P1. Number and percentage of patients enrolled per center
- P2. Number and percentage of patients stratified by gender; mean and median age, range and interquartile range;

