- P3. Number and percentage of patients stratified by race;
- P4. Number and percentage of patients stratified by educational level;
- P5. Number and percentage of patients stratified by working status;
- P6. Mean and median age, range and interquartile range of time since diagnosis of SM;
- P7. Number and percentage of patients undergoing pharmacological treatment for MS by active substance; mean and median, interquartile range and range of the dose and distribution of the frequency of treatment administration;
- P8. Number and percentage of patients undergoing concomitant pharmacological treatment by active substance; mean and median, interquartile range and range of the duration;
- P9. Mean and median, range and interquartile range of the total number of relapses from the diagnosis;
- P10. Mean and median, interquartile range and range of the total number of relapses in the last year;
- P11. Number and percentage of patients stratified for relevant previous and / or concomitant diseases; if previous, mean and median, range and interquartile range of duration; if ongoing, number and percentage of the diseases being treated;
- P12. Number and percentage of patients stratified by outcome (not performed / normal / abnormal) to physical examination in relation to:
 - a) General appearance;
 - b) Skin;
 - c) Head, neck, thyroid;
 - d) Ear, nose, throat;
 - e) Muscolo-skeletal;
 - f) Respiratory;

- g) Heart;
- h) Peripheral vascular;
- i) Gastrointestinal
- j) Abdomen, liver;
- k) Renal and genitourinary
- l) Endocrine / Metabolic
- m) Neurologic;
- n) Mental status;
- o) Other;

P13. Mean and median, interquartile range and range of height, weight and bmi value

P14. Mean and median, interquartile range and range of temperature, respiration rate, heart rate, maximum and minimum blood pressure;

P15. Mean and median, range and interquartile range of the number of episodes of acute exacerbation since the last visit;

P16. Mean and median, interquartile range and range of EDSS score;

P17. Mean and median, interquartile range and range of TSQM-9, all domains: effectiveness, convenience and global satisfaction;

P18. Change from baseline in the score of convenience satisfaction domain of TSQM-9 at 12 weeks;

P19. Change from baseline in the score of all domains of the TSQM-9 at 24 weeks;

P20. Adjusted repeated measures analysis of variance for change of convenience satisfaction domain of TSQM-9 at 12 and 24 weeks;

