P21. Number and percentage of patient who have correctly taken the prescribed doses of treatment within the last 28 days; if don't, mean and median, interquartile range and range of injections have not been performed during the last 28 days;

P22. Number and percentage of patients per reasons to non correctly taken the treatment:

- a) Anxiety for injection
- b) Skin reaction
- c) Forgot to take the dose
- d) Pain at the injection site

- e) Depression
- f) Headhache
- g) Fatigue
- h) Flu-like symptoms
- i) “I did not want to”
- j) “I am not sure of the benefits”
- k) “I am tired of injections”
- l) No one available for injection
- m) Uncomfortable dosing
- n) “I am pregnant / I have planned a pregnancy”
- o) Other

- P23. Mean and median, interquartile range and range of injections expected from the therapy taken in the last 28 days;
- P24. Mean and median, interquartile range and range of MSTCQ;
- P25. Change from baseline in the score of the MSTCQ at 12 and 24 weeks;
- P26. Adjusted repeated measures analysis of variance for change of the MSTCQ at 12 and 24 weeks;
- P27. Mean and median, interquartile range and range of MusiQol;
- P28. Change from baseline in the score of the MusiQol at 12 and 24 weeks;
- P29. Adjusted repeated measures analysis of variance for change of the MusiQol at 12 and 24 weeks;
- P30. Mean and median, interquartile range and range of FSS;
- P31. Change from baseline in the score of the FSS at 12 and 24 weeks;
- P32. Adjusted repeated measures analysis of variance for change of the FSS at 12 and 24 weeks;
- P33. Mean and median, interquartile range and range of EDSS;
- P34. Change from baseline in the score of the EDSS at 12 and 24 weeks;
- P35. ARR, Annualized Relapse Rate
- P36. Number and percentage of abnormalities in laboratory values per each test;
- P37. List of all laboratory abnormalities;
- P38. Number and percentage of adverse events stratified by severity;

	
Statistical Analysis Plan Protocol N. BIIT0215– Platinum
	
Pag. 18 di 18

--	---	---

- P39. List of all adverse events with related characteristics;
- P40. Number and percentage of patients who discontinued the study and reasons of discontinuity;
- P41. Number and percentage of patients who experienced pregnancy during the study and outcome of pregnancy.

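### The SAP does not define the response, the visits or the tested contrast of the primary repeated measures ANOVA, and neither natural reading of Table P20 gives a test of the week-12 change

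*SAP*

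**What the plan says.** The primary question, in protocol 6.2.1 and 16.1.1 and in SAP 11.a, is the change from baseline in the convenience domain at week 12. The trial has one arm and three assessments: T0, week 12 (T1) and week 24 (T2).

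The analysis is described in several places:

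- Protocol 16.3.3: "The primary endpoint (change of TSQM-9 convenience domain at week 12) will be analysed by a repeated measures analysis of variance", with adjustment for age, sex, disease duration, previous treatment duration and EDSS.
- SAP 11.a gives the command for the primary endpoint as "anova var1 time, repeated(time"). It does not say what var1 is or which visits time covers.
- SAP 11.b lists the secondary efficacy endpoints as changes from baseline and sends them, with the primary endpoint, to the adjusted repeated measures ANOVA.
- SAP 13, Table P20: "Adjusted repeated measures analysis of variance for change of convenience satisfaction domain of TSQM-9 at 12 and 24 weeks". P26 has the same form ("Adjusted repeated measures analysis of variance for change of the MSTCQ at 12 and 24 weeks"), as do P29 for MusiQoL and P32 for FSS.
- SAP 10 describes the method in general terms, as a comparison of means of a dependent variable over time. It sets the significance rule: "Differences will be considered statistically significant if the p-value will be less or equal to a type I error =0.05 (two-sided test").

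Table P18 lists the week-12 change but names no test. Neither document asks for a T1 minus T0 contrast, a test of the intercept or adjusted mean change, or a confidence interval.

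**The concern.** In a single-arm repeated measures ANOVA the p-value for improvement has to come from the time effect or from a named contrast. What the time effect tests depends on what is entered as the response and at which visits, and the SAP fixes neither.

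The wording of P20 invites two set-ups. One uses the changes at weeks 12 and 24, the other the scores at all three visits. Under the first, the time effect says nothing about improvement from baseline. Under the second, it mixes week 12 with week 24. In either case the tabled p-value could be read as the primary result when it answers another question. Because the choice is open, it could also be made after the data are seen. P26, P29 and P32 leave the same gap for the secondary questionnaires.

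**Working it through.** **Inputs.** From SAP 6: "with 250 subjects we have a power of 90% to detect a change of 3 points"; "under the conservative hypothesis of a SD=16 (9) for the difference between baseline and week 12"; "Assuming an average value of the overall convenience domain at baseline of 55 (SD=16"). From SAP 10: two-sided 0.05.

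Assumed: SD 16 at every visit, equal correlation r between visits, complete data, and a patient term in the ANOVA (the printed command shows none). With a common SD, the SD of a difference is 16 × √(2(1 − r)). This equals the planned 16 when r = 0.5, so 0.5 is the value consistent with the plan. With complete data, baseline covariates do not alter the within-patient time effect.

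**The plan's own figure.** Direct test of the week-12 change: 3 × √250 / 16 = 2.965, and Φ(2.965 − 1.960) = 0.84. The stated 90% is not reproduced two-sided; one-sided, Φ(2.965 − 1.645) = 0.91. That mismatch is a separate matter. The benchmark here is the 84% a direct two-sided test would have.

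**Reading A: response is the change at weeks 12 and 24.** Time has two levels, and (Y24 − Y0) − (Y12 − Y0) = Y24 − Y12, so baseline drops out. In a simulated dataset, the time-effect p-value on the changes and the paired t-test of week 24 against week 12 were both 0.21523.

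**Reading B: response is the change at week 12 only** (protocol 16.3.3 taken literally). Time has one level, so there is no time effect.

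**Reading C: response is the score at T0, T1 and T2.** The time effect has 2 df and tests any difference among the three means. Its noncentrality is λ = n × Σ(μ − mean μ)² / (256(1 − r)). For means 55/55/58 the average is 56 and the sum of squares is 1 + 1 + 4 = 6, so λ = 250 × 6 / 128 = 11.7. The noncentral F on 2 and 498 df gives 0.87.

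**Reading D: response is the score at T0 and week 12 only.** The time effect equals the paired t-test of week 12 against baseline (p = 0.00115 from both in a simulated dataset). This does test the primary endpoint.

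**Share of simulated trials with p ≤ 0.05** (20,000 per row, n = 250, r = 0.5):

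| True means T0/T1/T2 | A: changes | D: week 12 v baseline | C: three-visit scores |
|---|---|---|---|
| 55/55/55 | 5.4% | 4.9% | 5.1% |
| 55/58/58 | 5.1% | 83.3% | 86.7% |
| 55/75/75 | 4.9% | 100% | 100% |
| 55/55/58 | 83.6% | 5.1% | 87.2% |

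**Range over the assumed correlation.** For 55/55/58 with score SD 16:

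- Reading C: λ = 1500 / (256(1 − r)) is 8.4, 11.7 and 19.5 for r = 0.3, 0.5 and 0.7, giving 74%, 87% and 98% significant.
- Reading A: the T2 − T1 difference has SD 18.9, 16.0 and 12.4, giving 70%, 84% and 97%.

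The 5% rate under reading A when the two changes are equal does not depend on r.

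**The case against.** A reader might infer that the plan does test week 24 against week 12 in place of improvement from baseline. The documents do not support so firm a statement. var1 is never defined, and P20 is a one-line table title that could loosely describe the output of a model of scores. Protocol 16.3.3 names the endpoint and then the method; it does not say that change scores are entered, and it mentions week 12 only. The description in SAP 10 and the command in SAP 11.a fit scores across visits better, since a week-12 change has no second time level. With scores at T0 and week 12 the time effect is the right test, and with three visits a sustained 3-point gain is detected about as often as by the direct contrast (86.7% against 83.3%).

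All of that stands, and it limits the point to what the SAP leaves open. It does not remove it. The two-visit score model is stated nowhere, and P20 covers weeks 12 and 24. The three-visit score model cannot attribute a significant result to week 12. The mixed model in SAP 10 is offered only as possibly useful and comes with no contrast.

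It would also go too far to say that a change score must not be the response. With centred covariates, such a model can test the adjusted mean change at week 12. The SAP does not request that test.

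**Conclusion.** The concern holds as a gap in specification that bears on the primary result. The response, the visits and the contrast are undefined, and P20's scope leads to one of two tests that do not isolate week 12.

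- With changes as the response, a sustained gain is significant in about 5% of trials, and a week-12 null followed by a 3-point rise at week 24 in about 84%.
- With three-visit scores, that same week-12 null is significant in about 87%.

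These figures are conditional on the reading, on n = 250 and SD 16 from the plan, and on an assumed correlation of 0.5. Over correlations of 0.3 to 0.7 the last two run from 70% to 97% and from 74% to 98%. They show what each reading would do; they are not evidence that the sponsor intends either. The algebra for changes and the 2-df nature of the three-visit test do not depend on these assumptions.

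**What to change.** In SAP 10 and 11, define var1 and the visits entered, preferably the score at T0, T1 and T2 with time as a categorical factor. Name the adjusted T1 minus T0 mean difference in convenience, with its 95% CI and two-sided p-value, as the primary result. Name T2 minus T0 for the week-24 results. A change-score model with centred covariates and an explicit test of the adjusted mean change at week 12 would also do, provided the SAP says so.

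Retitle P20, P26, P29 and P32 to report these contrasts, and align protocol 16.3.3 at the next amendment. The cost is wording and table titles only; no new data, visits or patients are needed. It should be done before the data are analysed.

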## 5. INTRODUCTION

Multiple sclerosis is a chronic autoimmune and neurodegenerative disorder of the central nervous system characterized by inflammation, myelin destruction, and axonal damage with subsequent oligodendrocyte and neuronal loss (1).

Relapsing-remitting MS is the most common clinical presentation of the disease. Patients with relapsing MS experience discrete episodes of neurological dysfunction (referred to as relapses, exacerbations, or attacks) each lasting several days to several weeks, which occur intermittently over many years (2).

The currently available IFN- $\beta$  therapies and GA both require either intramuscular (IM) or subcutaneous (SC) injections, from as few as once a week (IFN  $\beta$ -1a im to as many as 3 times to 4 times a week (IFN  $\beta$ -1a SC, IFN  $\beta$ -1b SC), and 7 times a week (GA SC) (3).

Despite the benefits of disease-modifying therapies (DMTs) for MS, several problems are associated with their use, including inconvenient methods and schedules of administration, long periods of therapy, and significant side effects (4).

In particular, the high frequency of injections required often produces discomfort interfering with patients' activities of daily living, and may lead to refusal or inability to accept or adhere to these therapies. In fact, the proportion of non-adherent patients on DMTs has been reported to be as high as 45%. (5, 6)

Devonshire et al. examined reasons for discontinuation of therapy in a multicenter study of adherence to IFN $\beta$ -1a im, IFN $\beta$ -1a sc, IFN $\beta$ -1b sc, and GA sc. Adherence was associated with female gender, ease of administration, satisfaction with therapy, treatment at a dedicated MS center, and family support (5).

Satisfaction with treatment is a variable recently incorporated into health outcomes research, not only due to its value for health care evaluation, but also for its implications in clinical practice. It is known that patients who are satisfied with their treatment show better compliance with prescriptions and play an active role in their own care (7).

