injectable subcutaneous Interferons. In such a context, as a primary objective this phase IV, interventional, multicenter study aims at evaluating if Peg-IFN 125 µg subcutaneous (SC) every 2 weeks improves satisfaction and adherence in RRMS patients unsatisfied with others injectable subcutaneous Interferons. In addition, the study may provide data on Peg-IFN effects on health-related quality of life and other relevant patients' reported outcomes.

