## **8. STUDY POPULATION**

### **8.1. Inclusion Criteria**

To be eligible to participate in this study, candidates must meet the following eligibility criteria at Baseline (T0):

1. Ability to understand the purpose and risks of the study and provide signed and dated informed consent and authorization to use protected health information (PHI) in accordance with national and local subject privacy regulations.
2. Aged between 18 and 65 years old inclusive, at the time of informed consent.
3. Subjects diagnosed with Relapsing Remitting MS according to 2010 McDonald criteria.
4. Subjects with EDSS score between 0.0 and 5.0 at baseline.
5. Treatment with injectable subcutaneous Interferons with score < 58 in the “convenience satisfaction” domain of TSQM-9.
6. Period of stability from last relapse of at least 30 days before the baseline visit.
7. Treatment with intravenous corticosteroids completed at least 30 days before the baseline visit (assumption of oral cortisone allowed as long as within 4 mg per day for no longer than 3 days).

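### The SAP defines no adherence score, and its only 28-day adherence measures depend on injection frequency, so an all-or-none reading would show a rise after the switch even if patients skip injections at the same rate

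*SAP*

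**What the plan says.** SAP section 11.b lists the endpoint as "Changes from baseline in patient adherence to study treatment survey at 12 and 24 weeks" and assigns it, with all the others, to a covariate-adjusted repeated measures ANOVA. SAP section 8(b) and protocol section 13.1(b) describe the instrument in one sentence and give no scoring rule. The questionnaire is protocol Appendix C, whose content is not reproduced in the text available for review.

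The adherence measures appear only in SAP section 13:

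- P21 gives the "Number and percentage of patient who have correctly taken the prescribed doses of treatment within the last 28 days". For patients who did not, it summarises the "range of injections have not been performed during the last 28 days".
- P22 lists the reasons.
- P23 gives the "range of injections expected from the therapy taken in the last 28 days", as a separate descriptive table.

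Nothing divides the missed count by the expected count. MSTCQ, MusiQoL and FSS each have a change-from-baseline table and an adjusted ANOVA table (P25/P26, P28/P29, P31/P32). Adherence has neither.

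The regimen changes between the visits being compared. Patients enter on "Treatment with injectable subcutaneous Interferons with score < 58" in the convenience domain. Protocol section 7.1 places the baseline questionnaires in the two weeks before Peg-IFN starts, so the baseline look-back covers the previous drug. Protocol section 5 puts the subcutaneous interferons at "as many as 3 times to 4 times a week". Section 10.1 puts Peg-IFN at one injection every two weeks.

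**The concern.** A patient who must get 12 to 16 injections right to count as fully adherent at baseline needs only 2 at weeks 12 and 24. The count of missed injections can reach 12 to 16 at baseline and cannot exceed 2 on Peg-IFN. Either measure can therefore move because the number of opportunities to miss has changed, and neither document mentions that imbalance.

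This matters because the trial has one arm: the before/after contrast is its only evidence on adherence. Protocol section 5.2 says the study asks whether Peg-IFN "improves satisfaction and adherence in RRMS patients unsatisfied with others injectable subcutaneous Interferons", and SAP section 1 says the results are intended for publication. Adherence is also to be related to satisfaction by a Spearman correlation. SAP section 11.b gives only the generic command and does not say whether visits are kept separate. If they were pooled, two variables that both shift at the switch would be correlated partly for that reason.

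**Working it through.** The plan states no adherence figure, effect size or power, so there is nothing of its own to reproduce.

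**Inputs.** Injections due in 28 days: 3 x 4 = 12 to 4 x 4 = 16 on subcutaneous interferon (protocol section 5), and 28/14 = 2 on Peg-IFN (section 10.1). The skip rate per injection, p, is an assumption held equal on both drugs, because the documents give none. One anchor is the non-adherence of up to 45% cited in protocol section 5. If that were a 28-day all-doses figure with independent misses (also an assumption), p would be 1 - 0.55^(1/12) = 4.9% to 1 - 0.55^(1/16) = 3.7%.

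**Share with no missed injection (all-or-none reading of P21).** With independent misses this is (1 - p)^n. At p = 5%: 0.95^12 = 54.0%, 0.95^16 = 44.0%, 0.95^2 = 90.25%. If misses cluster within patients, a beta-binomial with intra-patient correlation r gives B(a, b + n)/B(a, b), where a = p(1/r - 1) and b = (1 - p)(1/r - 1). For n = 2 this reduces to (1 - p)^2 + r p(1 - p); at p = 5% and r = 0.3 it is 0.9025 + 0.3 x 0.0475 = 91.7%.

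| p | r | 12 due | 16 due | 2 due | Apparent gain (points) |
|---|---|---|---|---|---|
| 2% | 0 | 78.5% | 72.4% | 96.0% | 17.6 to 23.7 |
| 2% | 0.3 | 91.0% | 89.9% | 96.6% | 5.6 to 6.7 |
| 2% | 0.5 | 94.0% | 93.4% | 97.0% | 3.1 to 3.6 |
| 5% | 0 | 54.0% | 44.0% | 90.2% | 36.2 to 46.2 |
| 5% | 0.3 | 78.8% | 76.5% | 91.7% | 12.8 to 15.1 |
| 5% | 0.5 | 85.5% | 84.3% | 92.6% | 7.2 to 8.3 |
| 10% | 0 | 28.2% | 18.5% | 81.0% | 52.8 to 62.5 |
| 10% | 0.5 | 72.7% | 70.7% | 85.5% | 12.8 to 14.8 |

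Under all-or-none scoring the direction is constant. The gap closes only when each patient misses either every injection or none.

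**Missed count.** The expected count is n x p. At p = 5% it is 0.6 to 0.8 at baseline and 0.1 on Peg-IFN. P21 reports the count only for patients who missed some, so the relevant mean is np/[1 - (1 - p)^n]: 1.31 to 1.43 at baseline and 1.03 on Peg-IFN, with independent misses.

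**Alternative reading: a threshold.** Suppose correct taking meant at least 80% of doses. That allows 2 misses of 12, 3 of 16 and none of 2. With independent misses at p = 5%, 98.0% (12 due) and 99.3% (16 due) qualify at baseline against 90.2% on Peg-IFN, so adherence would appear to fall. The same reversal occurs at p = 2% and 10%. At p = 20% it does not (55.8% and 59.8% against 64.0%).

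**Proposed score.** The expected value of 1 - missed/expected is 1 - p whatever n is. At p = 5% it is 95% at every visit, and the expected change is 0.

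**The case against.** A reader might infer that the SAP commits to this measure and will report a large false improvement. The documents do not support that. P21 is a descriptive table produced by visit, and no text names its percentage or count as the variable in the ANOVA. What counts as correct taking is undefined. All-or-none is the natural reading, since everyone else is described by injections not performed, but Appendix C cannot be checked and a threshold could reverse the sign. The largest gains also need independent misses. Realistic clustering cuts them sharply, to 3 or 4 points at p = 2% and r = 0.5.

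A second objection concerns the question being asked. Whether a patient took everything prescribed over 28 days is a legitimate patient-level question, and fewer chances to miss may be part of what a less frequent regimen offers; protocol section 5.2 argues along those lines. The ratio answers a different question and weights one missed fortnightly injection as half the window. This stands as a reason to keep the all-doses percentage, but not to read its change as better behaviour per injection.

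Readers would also see some context. P23 shows the expected injections and P7 the administration frequency, and the protocol provides for pen accountability, although the SAP tabulates none of it.

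A reader of protocol section 5.2 might take adherence to be part of the primary objective. Sections 6.1.1 and 6.2.1 confine that to satisfaction and the TSQM-9 convenience domain. The correlation problem arises only if visits are pooled, which the SAP neither says nor excludes.

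**Conclusion.** The point holds in conditional form. No adherence score is defined, and the only measures specified depend on a number of injections due that falls six- to eight-fold between baseline and follow-up. If P21 is all-or-none and is used for the change from baseline, adherence rises in expectation with unchanged behaviour. For skip rates of 2% to 10% and intra-patient correlations of 0 to 0.5, the rise runs from about 3 to 63 points. That range rests on an assumed equal skip rate before and after the switch and on assumed clustering, so the documents do not establish that the artefact is large. The direction itself depends on the all-or-none reading. This should be fixed because it bears on any claim of improved adherence. It is confined to a secondary endpoint and leaves the primary analysis and sample size untouched.

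**What to change.** In SAP sections 8(b), 11.b and 13, define adherence per patient and visit as 100 x (1 - injections missed / injections expected in the last 28 days), from the counts already planned for P21 and P23. State what counts as a correctly taken dose. Use this proportion for the change from baseline at weeks 12 and 24 and, within visit, for the Spearman correlation with satisfaction. A binomial mixed model of missed out of expected, with a patient random effect, is one suitable analysis. Keep the all-doses percentage by visit, shown beside the expected number of injections, and state that its change is not to be interpreted as improved adherence per injection.

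The cost is SAP wording and one derived variable, with no new data. With two injections expected, the Peg-IFN value can only be 0, 50 or 100%, and the apparent gain in adherence will be smaller than on the all-doses measure.
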